5. STUDY PROCEDURES

Pre-Implant

- Patients will be screened for study
- Pre-implant ECG reviewed (to be performed on day of screening)
- Baseline transthoracic echocardiogram (TTE) reviewed (does *not* need to be performed during inpatient hospitalization; outpatient or outside-hospital TTE report may also be performed)
- Patients who screen-in will be provided Kansas City Cardiomyopathy Questionnaire
- NYHA functional class to be determined by treating physician
- Operating physician will be informed of patient allocation to facilitate planning of procedure

Randomization, Implant, and Periprocedure Care

- RA and RV leads will be positioned per routine
 - o Arterial access for CS angiography or LV septal mapping may be performed at the discretion of the implanting physician in order to facilitate optimal lead placement

- 'LV' lead will be positioned in CS or at His-bundle based on allocation assignment
 - o The allocation assignment will be based on randomization schedule (developed using random number generator)
 - o The study coordinator will keep allocations in a sealed envelope and provide to implanting physician at time of procedure
 - o Patients with LBBB and non-LBBB will be randomized separately
 - o Each independent site will maintain their own randomization schedule
- If the initial allocated site is unsuccessful, alternative site will be pursued
- Intracardiac EGM information (surface QRS to LV site or QLV), pacing output, and lead position at final site will be recorded
- Predischarge ECG performed
- Predischarge device interrogation will be performed (as per standard of care)

2-Week Incision Check

- As per routine post-device care, all patients will be scheduled for routine postoperative device check at 2 weeks to evaluate incision
- Device interrogation (as per standard of care)

1-Month Visit

- Routine device interrogation
- Routine clinical check

(Note: Week 2 and Month 1 visits may be combined, per treating doctor discretion, for the simple post-op wound and clinical visit)

3-Month Visit

- Routine ECG
- Routine device interrogation
- Routine clinical check

6-Month Visit

- Post-implant TTE
- Routine ECG
- Routine device interrogation
- Routine clinical check
- Administration of Kansas City Cardiomyopathy Questionnaire
- NYHA functional class to be determined by treating physician

12-Month Visit

- Post-implant TTE
- Routine ECG
- Routine device interrogation
- Routine clinical check

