6. STATISTICAL PLAN AND CONSIDERATIONS

Sample size estimation:

The sample size for this study is a total of 40 subjects (20 HBP and 20 CS lead). The sample size estimate was based on a goal to observe an absolute 10% difference in LVEF between the two groups, leading to a Cohen's d statistic of 1. With a significance level (α) = 0.05 and a power of 0.8, at least 17 subjects will be required in each group. A goal of 40 subjects was made to allow for possible dropout during the study period.

Statistical methods:

Patients will be studied based on the final treatment allocation. Crossovers and reasons for crossover will also be recorded. Fisher's exact or the Chi-Square test will be used for categorical variables, and continuous parameters will be compared by the two-tailed unpaired Student's t test and the F test for analysis of variance (ANOVA), as needed. Kaplan-Meier method will be used for computing the event free survival curves. Each implant strategy will be compared within this cohort of patients for its impact on percent change QRS duration, LVEF, and as clinical outcome. Multiple logistic regression and multiple regressions using the Cox proportional hazards model will be performed to determine the independent association of each of the implant variables with LVEF and clinical outcome.

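### The planned logistic and Cox models of implant variables have too few events in 40 patients and use post-randomisation measures that overlap with treatment, so they cannot show independent effects

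*Combined protocol and SAP*

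**What the plan says.** Section 6, Statistical methods, of the combined protocol and SAP states: "Multiple logistic regression and multiple regressions using the Cox proportional hazards model will be performed". The stated purpose is to establish the "independent association of each of the implant variables with LVEF and clinical outcome". The section gives no covariate list, limit on the number of terms, penalisation, projected event count or exploratory label.

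The term implant variables is not defined. The nearest list is in Section 5, Randomization, Implant, and Periprocedure Care: "Intracardiac EGM information (surface QRS to LV site or QLV), pacing output, and lead position at final site will be recorded".

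Three other provisions matter here:

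- **Sample size (Section 6).** The trial is sized only for a two-group LVEF comparison, on "an absolute 10% difference in LVEF between the two groups, leading to a Cohen's d statistic of 1".
- **Grouping (Section 6, with Sections 2 and 5).** Patients are analysed by the treatment they finally have, and crossover at implant is allowed in both directions.
- **Clinical outcome (Section 2, Primary endpoints).** This is a 12-month composite of heart failure admission, ventricular tachyarrhythmia and death from any cause.

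**The concern.** There are three separate difficulties.

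1. **Too few events.** The precision of a Cox or logistic model depends on the number of events (for logistic regression, the size of the smaller outcome class), not on the number of patients. Several covariates on a handful of events give unstable coefficients.
2. **Overlap with treatment.** The implant variables are measured after randomisation, at a site determined by the treatment delivered. If treatment is in the model, its effect is conditioned on its own consequences. If it is left out, the implant variables partly stand in for it. Neither version yields an association that is independent of treatment.
3. **Outcome type.** LVEF is a continuous measure, and logistic and Cox models do not apply to it without a cut-off or an event definition.

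The practical risk is that a report names predictors of response, or quotes adjusted hazard ratios, that rest on a few events and on variables entangled with the pacing strategy.

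**Working it through.** **Inputs from the documents.** 40 patients, 20 per arm; a 10-point LVEF difference with d = 1, so an SD of 10 points; two-sided alpha 0.05; power 0.80; at least three candidate implant variables (Section 5).

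**Assumptions (not in the documents).** A 12-month composite risk of 10-50%; 10 events per variable as a conventional benchmark, with 5 as a lenient one; correlations and crossover rates as stated below.

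**1. The plan's own figure.** The plan says "With a significance level (α) = 0.05 and a power of 0.8, at least 17 subjects will be required in each group". For d = 1, a two-sided t test with n per group has noncentrality d × √(n/2). Exact power is 0.781 at n = 16, 0.807 at n = 17 and 0.869 at n = 20. The figure of 17 reproduces. It supports a two-group comparison and says nothing about a multivariable model.

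**2. Events per variable.** Events = 40 × risk; events per variable = events ÷ number of variables.

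| Assumed risk | Events | 3 variables | 4 variables | Covariates supported at 10 per variable | At 5 per variable |
|---|---|---|---|---|---|
| 10% | 4 | 1.3 | 1.0 | 0 | 0 |
| 20% | 8 | 2.7 | 2.0 | 0 | 1 |
| 30% | 12 | 4.0 | 3.0 | 1 | 2 |
| 40% | 16 | 5.3 | 4.0 | 1 | 3 |
| 50% | 20 | 6.7 | 5.0 | 2 | 4 |

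Three variables at 10 events each need 30 events, or 30/40 = 75% of patients. In a logistic model the smaller outcome class is at most 20 of 40, so the best case with three variables is 20/3 = 6.7 whatever the event rate.

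**3. Information on the composite even with one covariate.** By Schoenfeld's formula, 80% power for a hazard ratio of 0.5 with equal groups needs 4 × (1.960 + 0.842)² ÷ (ln 0.5)² = 65.3, so 66 events. Power is about 10% at 4 events, 16% at 8, 22% at 12 and 34% at 20.

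**4. Overlap with treatment.** In an analysis by final treatment, CS-versus-His position is the treatment variable, so the two cannot both be estimated. Against the assigned arm the overlap is incomplete. With 20 per arm, crossover only from HBP, and k patients finally on HBP, r² = k/(40 − k) and the variance inflation factor is 1/(1 − r²):

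- 10% crossover: k = 18, r = 0.90, inflation 5.5
- 30% crossover: k = 14, r = 0.73, inflation 2.2
- 50% crossover: k = 10, r = 0.58, inflation 1.5

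**5. Illustration of instability.** Null Cox trials of 40 patients were simulated (1,000 per setting) with treatment plus three implant variables, assumed to correlate 0.7, 0.7 and 0.5 with treatment. The central 95% range of the estimated treatment hazard ratio (true value 1) was:

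| Assumed risk | Treatment alone | Treatment plus three |
|---|---|---|
| 20% | 0.19-4.8 | 0.03-28.9 |
| 30% | 0.28-3.5 | 0.08-18.6 |
| 50% | 0.41-2.6 | 0.16-8.3 |

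The widening reflects both the few events and the assumed correlations. It applies only if treatment is put in the same model.

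**6. LVEF.** The endpoint in Section 2 is change in LVEF, with no responder definition. Section 1 mentions recovery to an LVEF of at least 50% as a usual description of hyper-response, but no endpoint adopts it.

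**The case against.** The strongest reply is that this is a supporting analysis with its own aim. The groups are compared by other means: "continuous parameters will be compared by the two-tailed unpaired Student's t test", with categorical tests and Kaplan-Meier curves alongside. That stands, and it rules out several stronger readings.

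- **A reader might infer that the implant variables are fixed by the assigned arm.** They are not. Crossover is allowed both ways and patients are analysed by final treatment. Only CS-versus-His position is determined by treatment, and it follows treatment received. QLV and pacing output can vary within an arm, and the documents give no correlation with arm.
- **A reader might infer that the plan adjusts the treatment effect for these variables.** The text gives no model formula and does not say that treatment is included. The ranges in step 5 of the working show what would happen if it were.
- **A reader might infer that the LVEF comparison loses power.** The planned t test is unaffected by a separate association model.

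Two further points stand. The event count and number of covariates are not in the documents, so the size of the problem rests on assumptions, and one covariate, or two near 50% risk with no dropout, could meet the 10-event benchmark. Events per variable also does not limit a linear LVEF model: at an assumed 10-20 patients per term, 40 patients could carry 2-4 terms.

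What the reply does not answer is that the plan promises an independent association for each implant variable, with no cap on model size. The shortage holds with only the three variables in Section 5, across the whole assumed range of risk.

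**Conclusion.** The concern holds in a limited form. With three implant variables and an assumed 12-month risk of 10-50%, there are 1.3-6.7 events per variable, and a logistic model cannot exceed 6.7. The candidate variables are post-randomisation measures tied in varying degree to the pacing site, and one of them contains treatment received. Coefficients from such models would be unstable and could not be read as independent effects. For LVEF, neither named model is applicable as written.

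This should be corrected, but it does not undermine the LVEF comparison that sized the trial. The conclusion rests on assumed event risks, a conventional events-per-variable benchmark, and Section 5 as the source of the undefined implant variables. The simulated ranges rest also on assumed correlations and on treatment being in the model.

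**What to change.** Revise Section 6, Statistical methods, as follows.

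1. **LVEF:** a linear model with arm, baseline LVEF and LBBB stratum, stating whether arm means assigned or received. Baseline LVEF and LBBB status are already collected, and LBBB is a randomisation stratum.
2. **Composite:** a Cox model with arm only, or a Firth-penalised Cox model with arm and LBBB.
3. **Implant variables:** define the list and keep these variables out of any model used for the arm comparison. Report them descriptively by arm, or in a model labelled exploratory with at most one or two prespecified variables. Remove the claim of independent association.

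The cost is wording and a little analysis work. The trial gives up multivariable predictor claims that its data could not support. The change does not make the composite informative: even arm alone has only about 10-34% power for a hazard ratio of 0.5 at 4-20 events, so that estimate should be reported with its interval and read cautiously.

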7. RISKS AND BENEFITS

Cardiac resynchronization has led to significant improvement in survival and freedom from HF hospitalization for patients with advanced HF and conduction delay. The problem of nonresponse remains high, and the goal of this study is to evaluate a possible means to overcome nonresponse by varying LV lead position. There are risks with both CS lead position and His-bundle pacing which include, but are not limited to, the risk for cardiac perforation, tamponade, lead dislodgement, fracture, and site infection. Early data²⁷ that two technologies are comparable with respect to risk profile. The benefit of identifying an additional suitable location for LV lead position would be to extend the benefit of CRT to a broader group of patients.

8. SAFETY AND ADVERSE EVENTS

Safety:

As noted above, periprocedural complications will be logged with respect to procedure, system-related, and lead-related events. Each site's complications will be independently reviewed at the midpoint by the site's primary investigators. Should there be a trend towards increased complication risk, the study will be halted.

Adverse Events:

As noted above, all adverse events associated with devices will be monitored periprocedurally and continuously through the study. The site's PIs will independently review all events at respective sites after randomization of 20 combined subjects in order to make a determination for continuance.

9. DATA HANDLING AND RECORD KEEPING

Data will be collected on paper by study coordinators and transcribed into an electronic database which will be maintained on-campus locations at UCLA, NWU, Geisinger, IU, Rush, Edward, Baptist Health, and UofC. Data will be managed by the PIs and study coordinators. Access to the data will be limited to site PIs and research coordinators only during the study enrollment period. All patient specific identifiers will be kept separate from the primary research database. The research database will be organized by a unique patient identifier.

10. STUDY MONITORING, AUDITING AND INSPECTING

All periprocedural complications and adverse events will be reviewed by PIs at study midpoint to ensure there is no significant difference in event rate between the study groups. Should there be significant differences, or if there should be a high overall event-rate out-of-line with the procedural norm for CRT, the study will be halted.

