3. SUBJECT SELECTION AND WITHDRAWAL

Sites:

Subjects selected for study will be recruited from eight sites: The University of Chicago Medical Center (Chicago, IL), the Ronald Reagan UCLA Medical Center (Los Angeles, CA), Northwestern University's Northwestern Memorial Hospital (Chicago, IL), Geisinger Cardiology of the Geisinger Health System (Wilkes-Barre, PA), Indiana University Krannert Institute of Cardiology (Indianapolis, IN), Rush University Medical Center (Chicago, IL), Edward Elmhurst Healthcare Edward Hospital (Naperville, IL), Baptist Health Louisville (Louisville, KY). Each site will function independently but follow the same treatment protocol. Each site will maintain

their own randomization schedule. The data from the UCLA, NWU, Geisinger, IU, Rush, Edward, and Baptist Health sites will be shared with the University of Chicago at study completion for data analysis only.

Baptist Health Louisville has formally requested the University of Chicago IRB to serve as its own IRB. The following individuals from Baptist Health will be engaged the conduct of this study in Louisville with the following roles:

- [name] – Principle Investigator
- [name], APRN – Sub-Investigator
- [name] – Research Coordinator
- [name] – Research Coordinator

All of the study team members at Baptist Health have provided their curricula vitae, as well as confirmation of appropriate human subjects protection training.

Eligibility:

Eligible patients will be similar to those previously enrolled in the large randomized controlled trials which guide current indications for CRT. This includes:

- Patients at least 18 years of age
- LV systolic dysfunction with LVEF $\leq 35\%$
- Evidence of intraventricular conduction delay with QRS duration > 120 msec
- NYHA Class II, III, and ambulatory Class IV heart failure with either ischemic or nonischemic cardiomyopathy and patients with NYHA Class I symptoms and ischemic cardiomyopathy

Inclusion:

Inclusion criteria are identical to those presently accepted by the American Heart Association (AHA)-American College of Cardiology (ACC)-Heart Rhythm Society (HRS) for CRT.²⁸ These include:

- 1) Left ventricular ejection fraction (LVEF) $\leq 35\%$, sinus rhythm (SR), left bundle-branch block (LBBB) morphology, and QRS duration ≥ 150 msec, and NYHA Class II, III, or ambulatory Class IV patients on goal-directed medical therapy (GDMT) [Class I]
- 2) LVEF $\leq 35\%$, SR with LBBB with QRS 120-149 msec on GDMT [Class IIa]

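### Section 10's midpoint comparison of event rates between arms needs a combined two-arm table, and Sections 3 and 8 as written do not provide one

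*Combined protocol and SAP*

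**What the plan says.** Four sections of the combined protocol and SAP bear on the midpoint safety review.

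- **Section 10 (Study Monitoring, Auditing and Inspecting).** All periprocedural complications and adverse events are to be "reviewed by PIs at study midpoint to ensure there is no significant difference in event rate between the study groups". The halting condition is: "Should there be significant differences, or if there should be a high overall event-rate out-of-line with the procedural norm for CRT". No test, significance level or norm is given.
- **Section 8 (Safety and Adverse Events).** Each site's "complications will be independently reviewed at the midpoint" by that site's own investigators, who "will independently review all events at respective sites after randomization of 20 combined subjects". The halting condition here is: "Should there be a trend towards increased complication risk, the study will be halted". No arm, comparator or size is given.
- **Section 3 (Subject Selection and Withdrawal, Sites).** "Each site will function independently but follow the same treatment protocol". Data from the seven sites other than the University of Chicago "will be shared with the University of Chicago at study completion for data analysis only".
- **Section 9 (Data Handling and Record Keeping).** Paper data are "transcribed into an electronic database which will be maintained on-campus locations at" the eight institutions. During enrolment, access is confined to site PIs and research coordinators.

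**The concern.** The midpoint review is the only one in the plan with a stated halting rule. Section 10 makes that rule depend on a comparison of event rates between His bundle pacing (HBP) and coronary sinus (CS) pacing. Such a comparison needs event counts by arm from all sites, at the time when the 20th patient is randomised. Section 8 gives each investigator only the local events, and the one transfer of data that the plan describes comes at the end of the study. The risk is practical: the midpoint arrives, each site looks at two or three patients, and the comparison that Section 10 calls for is either not made or is improvised.

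A second, smaller difficulty is that Sections 8 and 10 state different triggers for the same consequence and do not say how they relate.

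**Working it through.** **1. Timing.** Section 6 plans 40 patients, 20 per arm. The midpoint is 40/2 = 20, which agrees with the count in Section 8. In Section 8 the word *combined* describes the number randomised. It does not say that events are pooled.

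**2. Who holds what at that moment.**

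| Needed for Section 10 | What the plan provides |
|---|---|
| Events from all eight sites | Section 8: each site's investigators review that site's events |
| Arm-level counts brought together | Section 3: the other seven sites' data go to the University of Chicago at the end, for analysis |
| A place where the counts are combined | Section 9: database kept on each campus; no combined interim table described |

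Section 10 does not say whether its PIs are the site PIs or the study's lead PIs. Either group would need counts from sites other than its own.

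**3. What a single site can show.** The documents give no accrual by site. With equal accrual (assumption), 20/8 = 2.5 patients per site. The most extreme result at a site with equal arms is every HBP patient with an event and no CS patient, or the reverse. With n patients per arm, the two-sided Fisher p is then 2/C(2n, n), and no other table at that site gives a smaller value.

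- 1 v 1: 2/2 = 1.00
- 2 v 2: 2/6 = 0.33
- 3 v 3: 2/20 = 0.10
- 4 v 4: 2/70 = 0.029

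A 1 v 2 site also has a minimum of 1/3 = 0.33. If one site took 40% of patients (assumption), it would have 0.40 × 20 = 8, or 4 v 4 if evenly split. It could then reach p < 0.05, but only if all four patients in one arm had an event and none in the other did. It would still say nothing about the other 12 patients. Fisher's test is used because Section 6 names it, with chi-square, for categorical variables. Section 10 itself names no test.

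**4. Whether the two triggers can differ.** Suppose both were applied to a pooled table of 10 v 10 (assumption; the plan does not fix the split at 20) with 4 events on HBP and none on CS:

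p = 2 × C(10,4)/C(20,4) = 2 × 210/4845 = 0.087.

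Many readers would call 4 v 0 a trend, but it is not significant at 0.05 (an assumed level). With no events on CS, significance needs 5 v 0: 2 × C(10,5)/C(20,5) = 2 × 252/15504 = 0.033. The example shows only that the wordings can lead to different decisions.

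**The case against.** The strongest reply is that the sections are compatible. Each states a sufficient condition for halting, and neither says that the study continues when its own condition is not met. They can be read as two tiers, a local review and then a joint one, with a halt if either is triggered. That stands, and a reader who infers a flat contradiction between Sections 8 and 10 goes further than the text. What remains is that no section describes the tiers or says how they relate.

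A reader might also infer that the plan forbids the PIs to see pooled counts. It does not. Section 9 leaves site PIs within the permitted group, and Section 3 can be read as governing the analysis data set, without expressly barring an exchange of safety counts. Knowing when the 20th patient has been randomised already presumes some contact between sites. But permission is not a procedure: no route for arm-level counts is written, and the only transfer that is written comes too late.

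Finally, it is tempting to attach probabilities of halting to each trigger. The documents do not support that. Section 8's trend belongs to a local review, its comparator is unstated, and it may mean an excess over the usual CRT complication rate, which would bring it close to Section 10's overall-rate condition. Any such probability would rest on definitions and event rates that the reader has to supply.

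In mitigation, the trial is small, uses approved devices, and monitors device-related adverse events continuously under Section 8. That bears on priority; it does not supply the missing table.

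**Conclusion.** The point holds as a gap between a required comparison and the means to make it. Section 10 calls for an arm comparison at 20 patients, and Sections 3 and 8, followed as written, leave no one with the table it needs. The finding about the missing table rests on the text alone. Its size, 2.5 patients per site and a minimum p of 0.33 at a 2 v 2 site, rests on equal accrual and on Fisher's test. A dominant site would relax the arithmetic but would not supply the other sites' counts. The differing triggers are an ambiguity to be resolved, with 4 v 0 as an illustration under an assumed 10 v 10 split and 0.05 level. The review concerns safety only, so no efficacy error rate is affected. This is a cheap improvement and no threat to the trial's main comparison.

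**What to change.** - At the 20th randomisation, each site sends the coordinating site a de-identified complication log showing randomised arm and treatment received. Both are needed because Section 2 permits crossover and Section 6 analyses by final treatment.
- The site PIs jointly review one combined two-arm table. Local review can continue alongside.
- Amend Section 3 to allow this transfer during enrolment. Section 9 needs no change, since its access limit already includes site PIs.
- Reconcile Sections 8 and 10 so that they state one review scope and one halting criterion, defined on the pooled table. The investigators should set the threshold and write it down before the review.

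The cost is a short amendment and one small data transfer per site, with no new staff or committee. The drawback is that PIs see interim safety counts by arm, which Section 10 already implies.
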